We have now decided to further develop the sensory input device as it is noninvasive and much less expensive for self-training. This Phase I SBIR research will determine the optimal stimulation device characteristics before using the device in Phase II studies for eliciting swallowing during self-training in patients with oropharyngeal dysphagia post stroke.

We have reviewed the FDA requirements for our device and it may qualify as a “*Therapeutic massagers and vibrators 890.5975*” under “*Physical medicine devices*” which are *Class I 510(k) exempt devices*. The IRBs that approved an ongoing study in healthy volunteers did not consider that an IDE was needed for use of this device.

This device is undergoing development; the results of this Phase I trial will be the basis for the selection of the motor type(s), holder design, strap, frequency, mode and duration of vibration. The engineers involved in the project will be developing the device to be used for Phase II using the results from this Phase I study.

A related vibrotactile device was included as the control device in a small Phase II study evaluating the use of an intramuscular implant device for swallowing retraining between 2005 and 2009 (IDE G060153). The vibrotactile device had comparable outcomes to the implant after 12 months of daily use by patients with dysphagia. Four patients used a vibrotactile device daily for swallowing retraining for a year without adverse events.

We will submit the protocol and human subjects consent submitted to the IRBs to the FDA for this study for use in post-stroke humans with dysphagia and await their decision regarding the need for an IDE or whether the device is *Class I 510(k) exempt*.

Data Safety and Monitoring Plan

Data integrity will be assured by using the LabTrack electronic notebook system in [name] lab which is on a secure backup server. This system meets FDA standards for data monitoring. Case Report Forms (CRF) will be setup with templates requiring entry of all essential data elements on each participant such as inclusion/exclusion criteria, consent records and records of visits, telephone contacts, and correspondence tracking each participant’s involvement in the research. The LabTrack system tracks all entries, the date and the identity and any data changes by user ID. All measures will be entered into data files on the Laboratory server by participant ID no.. The PI and speech pathologist will conduct monthly quality assurance reviews of the CRFs and data files.

The outcome measures of participants’ preferences will include their swallowing frequency during 10 minute periods containing short epochs of vibration to the neck area, swallowing onset times after stimulation onset and participant visual analogue scale ratings of their perceived urge to swallow during stimulation. Each of these data points will be measured from digitized Chart recordings and entered into data files by participant number in Labtrack and Excel.

Data Safety Monitoring:

During each hourly visit with a participant, we will be testing for the accumulation of secretions in the upper airway by asking participants to phonate during breaks between devices every 10-12 minutes. If a participant’s voice quality is judged by the speech pathologist to have a wet gurgly quality, we will instruct the participant to regurgitate into the oral cavity and then swipe suction the mouth. The CRF will include records of phonation testing at each break, the speech pathologist’s rating of the phonation and a record of whether oral suctioning was indicated and applied. All adverse events will be recorded during a test session in the CRF on encrypted Laptops connected by VPN to the LabTrack system on a server in [name] laboratory. Participants’ status at the end of each test session will be recorded in the CRF in LabTrack.

Participants or their caregivers will be contacted within 2 days following a test session to record their status and any difficulties following testing. The findings will be recorded in CRFs in LabTrack. All participants in the project will be asked to take their body temperature daily and to contact the PI or speech pathologist if their temperature is elevated for 3 days in sequence while participating in the project. If a participant has had an elevated temperature for 3 days in sequence they will be scheduled

to see the medical officer for the study, a [name], who is Medical Director of the Hospital Division at Rockingham Memorial Hospital, who will evaluate the patient.

Records of adverse events (AE) will be evaluated by the medical officer, [name], the Study Team and the JMU and RMH IRBs for participants in the protocol and submitted to the safety officer at NIDCD on a quarterly basis. Serious adverse events (SAE) will be evaluated by [name] and reported to the IRBs at JMU and RMH and the NIDCD Safety Officer within 10 days of their occurrence.

The IRBs will evaluate the reports of AEs/SAEs to determine if use of the device shows increased risk of aspiration pneumonia and other problems indicating that use of the device produces "more than minimal" risk.

ClinicalTrials.gov requirements

This is a Phase I safety intervention trial assessing participants' preferences on various device characteristics. None of the participants will be using any of the devices for self-training or dysphagia therapy in this trial. As this study is not a treatment trial, participants may continue their usual regimen of dysphagia therapy while participating in the study.

All participants will be monitored for AE/SAEs while participating in the study; it is expected that participants will undergo 3 or more visits of 1 hour each to provide feedback on the devices to the investigators over a 1-2 month period. On completion of the experiments a participant will be discharged from the study.

Human Subjects Protection for Aim 2: Identifying Delivery Points for Introducing Patients to Swallowing Self-training to be conducted by Passy Muir, Inc.

We will apply to the JMU IRB to determine if the research to be conducted for Aim 2 qualifies under Exemption 2 as exempt from the DHHS human subjects regulations the DHHS regulations as it only involves survey and interview procedures that do not involve (i) information obtained that is recorded in such a manner that human subjects can be identified, directly or through identifiers linked to the subjects; and (ii) any disclosure of the human subjects' responses outside the research that could reasonably place the subjects at risk of criminal or civil liability or be damaging to the subjects' financial standing, employability, or reputation.

References

4. Langmore SE. *Endoscopic evaluation and treatment of swallowing disorders*. New York: Thieme; 2001.
5. Center EE-BP. Diagnosis and Treatment of Swallowing Disorders (Dysphagia) in Acute-Care Stroke Patients. *Evidence Report/Technology Assessment No. 8*. Vol AHCPR Publication No. 99-E024. Rockville, MD: Agency for Health Care Policy and Research; 1999.

Where will research be conducted? (Be specific; if research is being conducted off of JMU's campus a site letter of permission will be needed.)

Rockingham Memorial Hospital in the JMU-RMH Voice and swallowing Service

Will deception be used? If yes, provide the rationale for the deception:

no

What is the time frame of the study? (List the dates you plan on collecting data. This cannot be more than a year, and you cannot start conducting research until you get IRB approval.)

September 1, 2012

Data Analysis

What methodology will be taken to ensure the confidentiality of the data (i.e., how and where data will be stored/secured, how data will be analyzed, who will have access to data, and what will happen to data after the study is completed?)

Reporting Procedures

Professionals in dysphagia

Data Publication: Aim 1 will be published.

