[figure not shown]
Procedures/Research Design/Methodology/Timeframe

Research Design Aim 1:

Subjects: Patients with dysphagia post stroke will be recruited from the VS-CRF and inpatient and outpatient admissions post stroke. The videofluoroscopic records of patients who volunteer will be reviewed to determine if they have a score of 2 or greater on the Pen-Asp scale⁴⁷. Those without a videofluoroscopic study will receive the Mann Assessment of Swallowing Ability to identify those with a severity rating of “mild” or greater, that is a total numeric score of 177 or less^{48,49}. If a nasoendoscopic evaluation of swallowing has been conducted, that will also be reviewed to determine if there is evidence of risk of aspiration⁵⁰. (see Human Subjects protection).

i. Frequency Comparisons:

Motors at frequencies of 30, 70, 110, 150, and 70/110 Hz (using 2-6 kPa neck pressure) will apply 8 s of stimulation followed by 15 s rest for a total of 28 stimulation trials for a total of 10.7 minutes per condition. Optionally, other hybrid motors similar to the 70/110 Hz motor may be used. After a condition, the patient will mark on a visual analogue scale of 0 to 100 mm their *urge to swallow* and their comfort level with stimulation for that condition. Online recordings of bi-axial accelerometry of laryngeal motion, inductive plethysmography of respiration, and digital video recordings will identify laryngeal movement and respiratory apnea

[figure not shown]

to confirm swallows (Figure 4). Swallows cannot be identified during stimulation because of vibration interfering with the accelerometry signals, which necessitates video recording. The *rate of swallowing* in a 10.7 minute condition will be computed. The order of different frequencies will be counter-balanced across patients. Total testing time with rest periods will be 1 hour. If all the frequencies cannot be tested in the one hour time period, the remaining untested frequency (ies) can be completed at the end of another session if time allows, or the participants can attend additional sessions as needed. We expect that one frequency will be optimal across patients; if two frequencies are optimal we will combine them by using motors with different frequencies on each side.

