Aim 2. Identifying Delivery Points for Introducing Patients to Swallowing Self-training.

Background The Passy Muir Swallowing Self-Training device is a novel approach to dysphagia rehabilitation. It requires that speech pathologists are willing to augment a patient's rehabilitation by introducing a self-training device before discharge to home. As the majority of patients return home in the care of a family member post discharge⁹, the time before they are discharged is optimal for introducing a self re-training device as shown in Figure 6. Aim 2 is to obtain input from speech pathologists on the optimal time and method for introducing a swallowing self-trainer for patients with dysphagia post stroke. Speech pathologists' input on the development of methods for patient introduction and training is needed prior to Phase II. Points of discharge to home, either from acute

care, skilled nursing or rehabilitation are time points to introduce a home based self-training system to patients who continue to have swallowing disorders post stroke.

Will data be collected from or about any of the following populations?

- Minors (under 18 years of age); Specify Age: _____
- Prisoners
- Pregnant Women
- Fetuses
- Cognitively impaired persons
- Other protected or potentially vulnerable population
- Not Applicable

Humans Subjects protections information

Revised Human Subjects Protection for Aim 1: Identifying the optimal stimulation characteristics for increasing swallowing in dysphagic participants (Subcontract with James Madison University)

Risks to Human Subjects

a. Human subjects involvement, characteristics and design

Participants in the subcontract at James Madison University will include up to 40 adults who have been diagnosed as having a swallowing disorder following a stroke. Based on the Harrisonburg Health Community Survey 2011, it is estimated that 20% of seniors have had strokes in the Harrisonburg community, 2/3 of who are male. Figures from the U.S. Census 2011, and the *Virginia Atlas 2005* indicate that the population breakdown by race and ethnic categories are 78% Caucasian, 6% African American, 4% Asian, 16% Hispanic and 12% Other in the Harrisonburg area. We used these estimates in completing our enrollment table.

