The criteria for inclusion will include diagnosis of an oropharyngeal swallowing disorder (dysphagia) post stroke on instrumental examination including videofluoroscopy. We will limit recruitment to those persons who meet specific criteria for swallowing disorders based on published screening instruments (described below). We will recruit persons to come for screening or visit their home if that is more convenient for them. All participants will have had a modified barium swallow study within one year prior to participation in the study. If a participant has had a videofluoroscopic examination within the last year and is stable we will review that examination or the description to determine if they would have a score of 2 or greater on the Pen Asp Scale¹. This scale can be obtained from review of a videofluoroscopic examination and is the gold standard method of measurement of risk of aspiration. We will also use the Mann Assessment of Swallowing Ability (MASA) to screen for persons who continue to have dysphagia², recently found to have the highest sensitivity and specificity for identifying participants with aspiration on videofluoroscopy³. By including only participants with a Pen Asp score of 2 or greater or a MASA numerical score of 177 or less, only participants with mild or worse oropharyngeal dysphagia will be included in this research. A nasoendoscopic evaluation of swallowing may be administered if required for clinical care and ordered by a physician⁴. Participants will be carefully selected to only include those with some upper esophageal sphincter (UES) opening on videofluoroscopy to avoid including participants who would accumulate significant residue during the testing. Exclusions from the research will be participants with no UES opening, and other disorders such as traumatic brain injury, Parkinson disease, post head and neck surgery for cancer, chemoradiation for head and neck cancer, or a history of other events that could have affected neuromuscular innervation of the swallowing musculature such as coronary bypass, cervical spinal fusion or brain stem tumor excision. Participants with more than one stroke can be included.

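### The Aim 1 subject description admits volunteers without a videofluoroscopic study on a MASA score, while the Human Subjects section says all have had a swallow study and selects on sphincter opening seen on videofluoroscopy; the two need one eligibility rule

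*Protocol*

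**What the plan says.** Eligibility for Aim 1 is described in two main places, and a third section touches on it.

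- **Research Design Aim 1, Subjects.** Existing videofluoroscopic records are reviewed for a Pen-Asp score of at least 2. For volunteers with no such record, "Those without a videofluoroscopic study will receive the Mann Assessment of Swallowing Ability to identify those with a severity rating" of mild or worse, at 177 or less. A nasoendoscopic evaluation is also reviewed if one has been done. The paragraph ends by pointing to the Human Subjects section.
- **Risks to Human Subjects, part a (characteristics and design).** This section states: "All participants will have had a modified barium swallow study within one year prior to participation in the study". It says selection will "only include those with some upper esophageal sphincter (UES) opening on videofluoroscopy to avoid including participants who would accumulate significant residue" during the testing, and it lists absence of UES opening as an exclusion. On severity it says "By including only participants with a Pen Asp score of 2 or greater or a MASA numerical score of 177 or less", entrants will have mild or worse dysphagia. The part belongs to a section headed "Revised Human Subjects Protection for Aim 1: Identifying the optimal stimulation characteristics for increasing swallowing in dysphagic participants".
- **Potential Benefits of the Proposed Research to Human Subjects and Others.** Some participants may not have had their swallowing disorder identified before. They are screened by a speech-language pathologist and referred to the Medical Director of the Voice and Swallowing Service for an examination before inclusion. What that examination consists of is not stated.

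**The concern.** The Subjects paragraph expects some volunteers to have no videofluoroscopic study and gives them another way to meet the severity criterion. The Human Subjects section describes a study population in which nobody lacks a swallow study and everyone's UES opening has been seen on videofluoroscopy. Staff holding both texts have no single answer when a volunteer without a study makes contact.

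That contact is foreseeable. The recruitment section relies on newspaper advertisements and notices, has volunteers contact the team directly, and screens them by telephone against the inclusion criteria.

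What is at stake is a protective entry criterion. By the protocol's own account, the UES selection exists to keep out people who would build up significant residue while being tested. If staff treat the Subjects paragraph as enough for entry, someone whose UES opening is unknown could be tested.

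**Working it through.** No arithmetic applies. The check is to take one volunteer through both texts. Suppose a post-stroke patient has no videofluoroscopic study, a MASA total of 177 or less, and meets every other criterion.

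1. **Severity.** The Subjects paragraph is met through the MASA. The Human Subjects section is also met, since it accepts either a Pen-Asp or a MASA score. The cutoff is 177 in both places, so the threshold is not in dispute.
2. **Swallow study within one year.** The Subjects paragraph sets no such condition. The Human Subjects section states it of all participants, and this volunteer fails it. This step assumes that a modified barium swallow study is a videofluoroscopic study. The neighbouring sentences make that the natural reading, but the protocol does not define it.
3. **UES opening.** The Subjects paragraph does not mention it. The Human Subjects section requires some opening to be seen on videofluoroscopy, and this volunteer has nothing on which to see it. This step does not depend on the assumption in step 2.
4. **Is a study supplied later?** The Subjects paragraph sends the volunteer to the MASA. The Human Subjects section offers only nasoendoscopy, when clinically required and ordered by a physician. The Potential Benefits section offers an examination of unstated content, and only to people whose disorder had not been identified before. A patient with known dysphagia but no videofluoroscopic study is not covered by it. In the text available (some pages were removed before review), no sentence schedules a study.

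So if the Human Subjects section governs, the sentence about volunteers without a study has no eligible participant to apply to. If that sentence is a live route into the study, the statement about all participants is untrue and the UES criterion cannot be applied as written. Both cannot stand unchanged.

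Three other statements in the Human Subjects section were considered and are not relied on:

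- The inclusion criteria call for "diagnosis of an oropharyngeal swallowing disorder (dysphagia) post stroke on instrumental examination including videofluoroscopy". This may require videofluoroscopy, or may name it as one of a class of examinations.
- "If a participant has had a videofluoroscopic examination within the last year and is stable we will review that examination" may imply that not everyone has a study, or may only set stability as the condition for using a recent one.
- "We will also use the Mann Assessment of Swallowing Ability (MASA) to screen for persons who continue to have dysphagia" gives the MASA a screening role and does not say that it replaces the study.

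**The case against.** The strongest defence is that the texts can be read together. The Subjects paragraph sets only a severity threshold, does not say the MASA waives anything else, and refers the reader to a section marked as revised. The Human Subjects section uses the MASA to screen and then adds further conditions. Its one-year requirement is timed before participation, not before screening. A volunteer could therefore be screened by MASA and still have to satisfy the remaining criteria before testing, and the pre-inclusion examination in the Potential Benefits section fits such a staged process.

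Much of this stands. It makes it plausible that the Human Subjects section governs, and then nobody is wrongly admitted. But no sentence says which section prevails, the alternative route is left in place, and the examination is neither said to include videofluoroscopy nor offered to everyone who lacks a study.

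It is also fair that testing is well protected. Only saliva is swallowed, suction is available, phonation is checked every 10 to 12 minutes, a speech-language pathologist supervises, and participants are contacted within 2 days. These safeguards lower the risk, but they act during or after testing and do not establish UES status at entry.

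A reader might infer more than the documents support:

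- **That patients with no UES opening will be enrolled.** The protocol excludes them explicitly. The gap is about patients whose status is unknown.
- **That videofluoroscopy is unambiguously demanded in three separate places.** Only the UES sentence is both explicit and unconditional. The barium swallow sentence needs the reading in step 2, and the diagnosis sentence is loosely worded.
- **That the either/or severity rule makes the study optional.** It concerns severity and says nothing about whether the study is needed.
- **That the device comparisons are compromised.** Conditions are compared within patients, and nothing here shows an effect on those comparisons.

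**Conclusion.** The inconsistency is real and should be resolved. A patient without a videofluoroscopic study is provided for in one section and cannot satisfy the other as written. The conclusion rests on the UES sentence, which is explicit, and on the statement about all participants, which needs the natural but undefined reading of the barium swallow study.

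Confidence is high for the conflict in wording and does not extend to any harm. The documents do not say how many volunteers would lack a study. The number may be zero, for instance if the Human Subjects section is applied throughout, and the documents support no numerical range. The practical consequence is conditional: it arises only if staff take the Subjects paragraph as sufficient for entry.

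**What to change.** Reconcile the Subjects paragraph, the Human Subjects criteria and the Potential Benefits text into one eligibility rule. It should state whether a videofluoroscopic study is required of every participant before the first stimulation session. If it is not, the rule should state how the UES criterion is applied to those without one. If the Medical Director's examination is meant to fill the gap, its content should be given. The choice is for the sponsor and investigator.

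The Data Safety and Monitoring Plan says case report form templates covering the inclusion and exclusion criteria will be set up; these should follow the reconciled rule.

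The cost is a few sentences of protocol text and matching form entries. The downside is that somewhat fewer patients may qualify if the route without a study is dropped.

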ii. Mode Comparisons: Using the optimal frequency(ies) identified, we will compare the effects of continuous versus the 4 Hz pulsed modes for 10.7 minutes each in counter-balanced order across patients measuring the rate of swallowing and ratings of the urge to swallow to identify the most effective mode of stimulation.

iii. Pressure Comparisons: Using the Iowa Oral Performance Instrument to measure strap to neck pressure and calipers to measure neck tissue fat, the effects of 2, 4, and 6kPa on rate of swallowing and urge to swallow with 8 s stimulation at the optimal frequency and mode of stimulation will be measured.

iv. Stimulation Duration: We will determine the stimulation durations applied by patients when they are instructed to initiate swallowing during stimulation using the parameters identified for stimulation in i, ii and iii. The time required for them to

[figure not shown]
initiate swallowing after the onset of stimulation will be measured using air filled bellows wrapped around the neck to identify swallowing timing after stimulation onset (Figure 5). Air filled bellows are required as vibratory stimulation will interfere with accelerometry; we have used these bellows previously to identify swallowing in fMRI⁴². Additionally oral pressure sensor in using a small tube placed on the anterior tongue will may be used to identify swallows. Neck calipers will measure tissue thickness in the throat area overlying the thyroid cartilage which may affect sensory input. When the participant has completed their final session, they will mark on a visual analogue scale of 0 to 100 their level of interest in using the self-training device at home for swallowing therapy.

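### Studies i to iii are sized on stimulation versus no stimulation but contain only motor-on conditions, so they can rank settings but cannot estimate the increase the sample size assumes.

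*Protocol*

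**What the plan says.** The protocol, Research Design Aim 1, lists these conditions:

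- Study i (frequency): "Motors at frequencies of 30, 70, 110, 150, and 70/110 Hz". Each condition consists of 28 bursts of 8 s separated by 15 s pauses, lasting 10.7 minutes in all. Similar hybrid motors are optional.
- Study ii (mode): "we will compare the effects of continuous versus the 4 Hz pulsed modes for 10.7 minutes each".
- Study iii (pressure): "the effects of 2, 4, and 6kPa on rate of swallowing and urge to swallow". Here too each burst lasts 8 s, and the frequency and mode are those already chosen.

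No motor-off, sham or baseline condition appears there or under Assignment to Studies. The Data Safety and Monitoring Plan likewise defines the swallowing-frequency outcome over roughly 10-minute periods that contain vibration.

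Expected Outcomes and Power Analyses plans within-patient comparisons of mean rate and mean visual analogue score across conditions. It then assumes a change from 1.2 swallows/min without stimulation to 2.0 with it, an SD of differences of 0.9, a Bonferroni alpha of 0.025 for two measures, power of 0.80 and an effect size of 0.88. This gives 15 patients per experiment.

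On purpose, the Purpose section confines the study to finding optimal device characteristics and leaves the usefulness of the self-training device to Phase 2. The section on human subjects involvement makes feedback on device preferences the primary aim. The Human Subjects heading for Aim 1 reads "Identifying the optimal stimulation characteristics for increasing swallowing in dysphagic participants".

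**The concern.** The sample size belongs to a comparison that the design never makes. Choosing the best of five frequencies, then the better of two modes, then the best of three pressures always returns a winner, whether or not vibration does more than wearing the strap or sitting for ten minutes. If the settings give similar rates, the data fit two opposite readings: all of them raise swallowing, or none does.

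The 1.2/min figure cannot stand in as a comparator. It comes from healthy volunteers in air-puff studies, not from stroke patients with dysphagia wearing this device. The 15 s rests do not help either: they follow each 8 s burst inside an active condition, and Assignment to Studies counts swallows in the intervals after stimulation as the response.

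At stake is what may be said when the chosen settings go into the Phase II device, which Importance of the Knowledge to be Gained says will be built on these results.

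**Working it through.** **1. Reproduce the plan's figure.** Inputs from Expected Outcomes and Power Analyses: difference 2.0 − 1.2 = 0.8; SD of differences 0.9; alpha 0.025; power 0.80. Effect size = 0.8/0.9 = 0.889, printed as 0.88. Sidedness is not stated; two-sided is assumed.

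Paired t-test, noncentral t with n − 1 degrees of freedom and noncentrality d√n:

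| d | power, n = 14 | power, n = 15 |
|---|---|---|
| 0.88 | 0.766 | 0.803 |
| 0.889 | 0.775 | 0.812 |

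So n = 15 reproduces, for stimulation versus no stimulation.

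**2. Look for that contrast in the design.** Study i has five motor-on conditions, study ii two and study iii three. Motor-off conditions: none. The difference behind n = 15 is therefore not estimable at any n.

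**3. Power for the contrasts that are planned.** The protocol gives no expected difference between active settings, so the differences below are assumptions. SD of differences 0.9, two-sided alpha 0.025:

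| Assumed difference (/min) | power at n = 15 | n for power 0.80 |
|---|---|---|
| 0.8 | 0.81 | 15 |
| 0.6 | 0.54 | 24 |
| 0.4 | 0.25 | 51 |
| 0.2 | 0.07 | 195 |

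**4. What one motor-off condition in study iii would give.** For a single contrast fixed in advance, power is the n = 15 column of step 1, 0.803 to 0.812. Standard error = 0.9/√15 = 0.232. The 97.5% interval, which matches alpha 0.025, has half-width t(0.9875; 14) × 0.232 = 2.510 × 0.232 = 0.58/min. The 95% half-width is 2.145 × 0.232 = 0.50/min.

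If each of the three pressures is tested against off, alpha is 0.025/3 = 0.0083. With d = 0.88, power at n = 15 falls to 0.64 and n = 20 is needed.

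**5. Why the contrast must not depend on picking a winner.** Simulation assumptions: no true effect, SD of differences 0.9, equal and independent condition errors, 15 patients. Choosing the best of three pressures and testing it against off in the same patients biases the difference by about +0.14/min. A false claim of increase then occurs in 3.1% of trials instead of the nominal 1.25% (one tail of 0.025).

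**6. Time.** One condition = 28 × (8 + 15) s = 644 s = 10.73 min. Three take 32.2 min and four take 42.9 min, leaving about 17 min of the hour. The protocol does not state the length of study iii conditions; 10.7 min is assumed from studies i and ii.

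**The case against.** The strongest reply is that this is a device-parameter study. Its Purpose section limits it to finding optimal characteristics, and the primary aim stated under human subjects involvement is patients' preferences. Comparing active settings answers both. This stands. A reader might infer from the Aim 1 heading that demonstrating an increase is the trial's stated object, and hence that the trial fails its own aim. The documents do not support that: the object is to identify optimal characteristics, and the words about increasing swallowing are a premise of it.

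The reply does not dispose of the point. What the Purpose section leaves to Phase 2 is usefulness as a self-training device. It does not set aside the acute effect of vibration on swallowing rate and urge, which are the outcomes measured here. The sample size is also built on that acute effect.

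A second reply is that vibration is not without prior support. The protocol describes four patients who used a related vibrotactile device daily for a year, and a healthy-volunteer study under way with the same procedures. This is fair, so it would be too strong to say the settings go forward on no basis at all. But the earlier patient experience concerns training outcomes, not acute rate, and the text does not show whether the volunteer study has an off condition.

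A third reply concerns an added condition itself. An off pressure that differs from the on pressure would mix vibration with strap pressure. Accelerometry cannot identify swallows while the motor runs (8 of every 23 s, 35% of a condition) but works throughout when it is off. The spare 17 minutes must also hold set-up, caliper measurement, phonation checks and suctioning. All of these stand, and they shape the fix.

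**Conclusion.** The point holds as a mismatch between design and sample size. Fifteen patients per experiment is correct arithmetic for stimulation versus no stimulation, and studies i to iii contain no such comparison. They can rank settings, which serves the stated purpose. They cannot estimate the increase over unstimulated swallowing or urge on which the sample size and the Aim 1 premise rest, nor tell equally effective settings from equally ineffective ones. For the comparisons actually planned, power at 15 is 0.81 only if two active settings differ by as much as the assumed on-off effect; it is 0.54 at 0.6/min and 0.25 at 0.4/min.

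These figures assume that the protocol's SD of differences of 0.9, from healthy volunteers, applies to stroke patients and to differences between active settings, and that tests are two-sided. Figures and some pages of the document are not visible; nothing in the visible text refers to an off condition. This should be corrected, but it does not invalidate the ranking of settings.

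**What to change.** Preferred: add to study iii one motor-off condition with the strap worn, of the same length and with the same rate and urge measurements, counterbalanced with the three pressures. Then:

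- Pre-specify a single contrast that does not depend on which pressure wins: either motor-on versus motor-off at one pressure named in advance, or the mean of the three pressures versus off. The power of 0.80 to 0.81 and half-width of 0.58/min apply to the first; the second needs its own SD.
- Count swallows identically on and off, by video throughout or in the matched 15 s windows only.
- Report the interval at the level that matches the alpha (97.5% for 0.025).

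Cost: about 11 more minutes of testing per patient (32.2 to 42.9 min, if study iii conditions last 10.7 min), with an additional session for a patient who tires, plus a short protocol addition. For one contrast, no new patients, staff or equipment are needed.

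Alternative, at no testing cost: leave the conditions as they are, restate the power for the smallest difference between active settings worth detecting, and state that the trial will claim no increase over unstimulated swallowing.
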